9.2 Primary Endpoint

9.2.1 Primary Variable Analysis

The primary efficacy endpoint will be the proportion of subjects who meet all of the following criteria for the SPC at 52 weeks:

- Improvement in pain on weight-bearing at fusion site (≥ 20 mm reduction from baseline on 100 mm VAS)
- Absence of significant graft harvest site pain (< 20 mm on 100 mm VAS)
- Improvement in Foot and Ankle Ability Measure Activities of Daily Living subscale (FAAM-ADL) (≥ 8 points improvement from baseline)
- Absence of device related or procedure related SAEs (up to Week 52)
- Absence of secondary surgical or nonsurgical interventions intended to promote fusion (up to Week 52)

The primary analysis will assess a non-inferiority of AMPLEX to ABG, and it will be claimed if the lower bound of the 2-sided 90% CI for the difference of the proportions (AMPLEX minus ABG) is greater than -12.0%. The superiority will be claimed if the lower limit of the 2-sided 95% CI is greater than zero. The CI will be constructed with the normal approximation to the binomial. In addition, the response status for each component will be summarized.

A subject will be considered an SPC success if he/she meets all of the SPC criteria, otherwise, the subject will be considered an SPC failure. The SPC response status will be determined for 12, 24, and 52 weeks. The response status for the visit-based components (i.e., weight-bearing pain, graft harvest site pain, and FAAM-ADL) will be assessed for each time point based on the windowed analysis visits. The response status for the non-visit-based components (i.e., absence of device or procedure related SAEs and secondary interventions to promote fusion) will be assessed in a period up to the actual visit date that the corresponding visit-based variables for a particular analysis visit are collected. If the actual visit dates among the visit-based variables are different at the analysis visit, the latest visit date among them will be used to determine the period for the assessment of the non-visit-based variables. If any of the components of the SPC at an analysis visit is missing, the SPC response status will be considered missing for the analysis visit. Note that the graft harvest site pain will be collected only for the ABG group, and therefore, no data for this component will be recorded for the AMPLEX group.

For the primary analysis, the last available SPC response status will be used (i.e., the last observation carried forward; LOCF) if the SPC response status at 52 weeks is missing. If no SPC response status data are available at previous visits, the SPC response status at 52 weeks will be considered failure.

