### **1.3 Benefit / Risk Aspects**

Arthrodesis remains the most common surgical procedure for patients with debilitating ankle and hindfoot arthritis. Average nonunion rates remain high (10-15%) but can be substantially higher in patients with co-morbid factors such as diabetes and other metabolic diseases, obesity, smoking, age  $\geq 65$  and osteoporosis. The data with both ABG and bone graft replacement products, particularly in light of their nearly ubiquitous use in this setting and the apparent equivalence of their fusion rates, suggest that a major differentiator is the lack of pain, dysfunction and morbidity related to graft donor sites when bone graft replacement products are utilized.

The inclusion of patient reported outcomes, functional evaluations and quality of life assessments is therefore important in evaluating the differences between these approaches. The current clinical trial was designed with this in mind, incorporating both radiologic assessment of fusion rate and validated scales to assess pain and functional outcome.

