#### **4.2.2 Randomization**

Once written informed consent is obtained and eligibility is confirmed the subject can be randomized. Randomization must occur prior to surgery, with a recommendation to take place on the day of surgery or as close to the procedure as possible. Subjects will not be made aware of their randomization result prior to surgery.

Subjects will be randomly assigned on a two to one (2:1) basis to either the treatment group (AMPLEX) or the control group (ABG). Randomization will be stratified by clinical center, surgical site (hindfoot vs. ankle), and nonunion risk factors (none vs. any of: obesity, diabetes, previous hindfoot/ankle surgery, or smoking history). Permuted block randomization will be performed within strata. To minimize the opportunity for the sequence to be predicted, the block size will be variable. The randomization schedules for all strata will be generated in advance by an independent statistician who is not going to be involved in the study conduct using a computerized random number generator. Investigational sites will not have access to the randomization schedules.

Administration of randomization assignments will be accomplished using an electronic system. The study coordinator or a designee will obtain the randomization assignment per the provided randomization instructions. A copy of the randomization assignment will be maintained in the subject's file.

If, between the time of randomization and the beginning of surgery, the subject becomes ineligible or withdraws, the reason for failure to treat will be recorded in the subject's study records.

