### **9.1 Determination of Sample Size**

Assuming true success rates of the primary endpoint to be 60% for ABG and 62% for AMPLEX groups, 396 subjects are needed to maintain 85% power to demonstrate non-inferiority of AMPLEX to ABG with a non-inferiority margin of -12% at a type I error rate of 1-sided 5% in a 2:1 randomization (264 for AMPLEX and 132 for ABG). To account for approximately 15% lost to follow-up, a total of 480 subjects (320 for AMPLEX and 160 for ABG) will be randomized.

In this calculation, the true success rate for AMPLEX is assumed to be slightly higher than that for ABG because of the potential benefit for AMPLEX on the absence of significant graft harvest site pain component. The assumption on the true success rate for ABG is made based on the clinical endpoint results in DiGiovanni et al. (2013) and the Augment SSED (2015). These data indicate relatively high success rates for each component at Week 52, and the success rate as a composite endpoint is estimated as approximately 60% under the independence assumption among components.

In the determination of the non-inferiority margin, retaining at least 80% of the assumed success rate in ABG is considered clinically meaningful, because it is inherently linked with substantial benefit of eliminating risks associated with ABG. Therefore, the non-inferiority margin is set to -12%.

In addition, the CT radiographic fusion success rate at 52 weeks for ABG is assumed to be 70% to 75% based on 24 and 36 weeks data available in FDA Orthopaedic and Rehabilitation Devices Division (2011). Assuming that the true CT radiographic fusion success rate for AMPLEX is the same as for ABG, the power to demonstrate the non-inferiority in the CT radiographic fusion success as an independent test with 396 subjects is 79% to 83% at 1-sided 5% significance level using the non-inferiority margin of -12%.

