9.2.2 Sensitivity Analysis

The following sensitivity analyses will be conducted to assess the robustness of the primary analysis:

- As-treated analysis based on actually received treatment on the mITT analysis set
- Analysis on the ITT analysis set
- Analysis on the PP analysis set

The same analysis conducted for the primary analysis will be repeated for these sensitivity analyses.

In addition, sensitivity analyses using the following approaches for the handling of missing data will be conducted:

- Missing-equals-failure approach
- Multiple imputation
- Tipping point analysis

Missing-equals-failure approach:

All subjects with missing SPC status at 52 weeks will be considered failures.

Multiple imputation methods:

The missing data for each component of the SPC for 12, 24, and 52 weeks will be imputed sequentially by regression-based imputation models using treatment group, baseline characteristics, and outcomes from preceding visits as predictors. The missing SPC response status will be calculated based on the imputed data. This imputation procedure will be repeated 100 times, and the primary analysis method will be applied to each of the imputed datasets. A combined estimate of the difference of the proportions (AMPLEX minus ABG) and the corresponding two-sided 90% CI will be obtained by the methods described in Rubin (1987) (3).

Tipping point analyses:

Let n_{1m} and n_{2m} be the number of subjects with missing SPC response status at 52 weeks in AMPLEX and ABG group, respectively. The tipping point analysis will assess the non-inferiority in all possible combinations of missing data imputation (i.e., $(n_{1m}+1)*(n_{2m}+1)$ imputations), and the result will be presented graphically. Specifically, the horizontal and vertical axes of the graph will be the number of subjects imputed as success in AMPLEX group (i.e., ranges between 0 and n_{1m}) and the number of subjects imputed as success in ABG group (i.e., ranges between 0 and n_{2m}), respectively. The non-inferiority outcome (i.e., supportive or not supportive) will be plotted for each combination of the number of successes from each group in the graph by different symbols (e.g., a solid circle for supportive and an open circle for not supportive outcomes). Note that each result with the LOCF method (i.e., primary analysis) and with the missing-equals-failure approach will be represented as one of the combinations in the graph.

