The primary endpoint will also be analyzed for the following subgroups for the mITT analysis set, and the treatment group difference of the proportions of subjects with SPC success for each subgroup will be presented in forest plots.

- Demographic characteristics: age, gender, and race
- Baseline comorbidities: obesity, diabetes, previous ankle/hindfoot surgery, smoking history, primary etiology
- Surgical site: affected side, fusion site (single, double, triple, or ankle)
- Investigational site
- Geographical region (US or non-US)

The treatment group comparisons after controlling each factor listed above will be conducted by stratified analyses using the Mantel Haenszel method as sensitivity analyses.

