9.3.2 Other Secondary Endpoints

The following other secondary efficacy endpoints will be assessed without multiplicity adjustments.

- Proportion of subjects achieving CT radiographic fusion success at 12 and 24 weeks (in the absence of secondary surgical or nonsurgical interventions intended to promote fusion)
- Change from baseline in pain on weight-bearing at fusion site at 12, 24, and 52 weeks (>20 mm reduction from baseline on 100 mm VAS)

- ABG harvest site pain at 2, 6, 12, 24 and 52 weeks (<20 mm on 100 mm VAS)
- Change from baseline in FAAM-ADL at 12, 24 and 52 weeks
- SPC at 12 and 24 weeks
- Change from baseline in Short Form-12 (SF-12) at 24 and 52 weeks

The difference of the proportions of subjects achieving CT radiographic fusion success between treatment groups will be estimated with the 2-sided 90% and 95% confidence intervals at 12 and 24 weeks. Similarly, the difference of the proportions of subjects meeting all the criteria for SPC between treatment groups will also be estimated at 12 and 24 weeks. In addition, the response status for each component of SPC will also be summarized. The missing values will be left as missing.

The change from baseline in FAAM-ADL and weight-bearing pain at fusion site at 12, 24 and 52 weeks will be analyzed by repeated-measures analysis of covariance (ANCOVA) models that includes treatment, time, treatment-by-time interaction, baseline value, presence of non-union risk factors (none vs. any of obesity, diabetes, and previous ankle/hindfoot surgery, or smoking history) at baseline, and fusion sites (single, double, or triple hindfoot, or ankle). The adjusted changes from baseline and their difference between treatment groups will be estimated for each time point. The overall difference over 52 weeks will be estimated as the main effect for treatment in the model. In addition, the proportion of subjects achieving ≥ 8 points improvement from baseline in FAAM-ADL and the proportion of subjects achieving ≥ 20 mm reduction from baseline in weight-bearing pain at fusion site will be summarized by treatment group at each visit. The missing values will be left as missing.

The ABG harvest site pain at 2, 6, 12, 24 and 52 weeks will be summarized for the ABG group. The proportion of subjects with < 20 mm in ABG harvest site pain will also be summarized at each visit.

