10.7.3 Data Listings

Data listings will be prepared by treatment group for all subjects with any markedly abnormal vital sign values at any time-point (including baseline).

All vital sign values will be listed by subject ID and time point. Values determined abnormal by the investigator and markedly abnormal values will be flagged.

11 Interim analyses

No interim analysis is planned.

12 Deviations from protocol analysis

There is no deviation from the planned analysis described in the protocol.

13 References

- 1 DiGiovanni, C. W., Lin, S. S., Baumhauer, J. F., Daniels, T., Younger, Al., Glazebrook, M., Lynch, S. E., and the North American Orthopedic Foot and Ankle Study Group. (2013). Recombinant human platelet-derived growth factor-BB and beta-tricalcium phosphate (rhPDGF-BB/β-TCP): an alternative to autogenous bone graft. *Journal of Bone and Joint Surgery*, 95, 1184-1192.
- 2 Martin, R. L., Irrgang, J. J., Burdett, R. G., Conti, S. F., & Van Swearingen, J. M. (2005). Evidence of validity for the foot and ankle ability measure (FAAM). *Foot & Ankle International*, 26, 968-983.
- 3 Rubin, D. B. (1987). *Multiple Imputation for Nonresponse in Surveys*. New York: Wiley.
- 4 U.S. Food and Drug Administration. (2015). Proposed summary of safety and effectiveness data (SSED). Retrieved from http://www.accessdata.fda.gov/cdrh_docs/pdf10/P100006b.pdf

Appendices

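### The intervals that decide SPC and CT fusion ignore the randomization strata; this is conservative and forgoes a modest gain in power if the strata predict outcome

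*SAP*

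**What the plan says.** Protocol 4.2.2 states: "Randomization will be stratified by clinical center, surgical site (hindfoot vs. ankle), and nonunion risk factors", the last factor being none versus any of obesity, diabetes, previous hindfoot/ankle surgery or smoking history.

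The deciding analysis of SPC is a difference in proportions with a 90% interval for non-inferiority (margin -12 points) and a 95% interval for superiority. SAP 9.2.1 says: "The CI will be constructed with the normal approximation to the binomial". SAP 9.3.1 uses the same interval for CT fusion, and the protocol synopsis, 9.6.2 and 9.6.3 agree. No stratum term appears in any of them.

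Stratification enters these endpoints only in SAP 9.2.2: "The treatment group comparisons after controlling each factor listed above will be conducted by stratified analyses using the Mantel Haenszel method". The factors listed there include obesity, diabetes, previous surgery, smoking, fusion site and investigational site, each taken alone. The any/none risk grouping used for randomization is not listed, and neither is its cross-classification with surgical site. SAP 9.3.1 applies the same set to CT fusion.

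The repeated-measures models for FAAM-ADL and weight-bearing pain in SAP 9.3.2 do adjust. Their terms include "presence of non-union risk factors (none vs. any of obesity, diabetes, and previous ankle/hindfoot surgery, or smoking history) at baseline, and fusion sites".

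**The concern.** When allocation is balanced within strata that predict outcome, the difference in proportions varies less from trial to trial than an unstratified variance assumes. The interval is then too wide, the test runs below its nominal level, and some power is given up. Two measures that SPC dichotomizes, FAAM-ADL and weight-bearing pain, are adjusted for both clinical factors in their secondary models but not in the deciding test, and the plan gives no reason.

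The case is stronger for CT fusion than for SPC. Protocol 1.3 says that nonunion rates "can be substantially higher in patients with co-morbid factors such as diabetes and other metabolic diseases, obesity, smoking", which covers three of the four factors in the risk stratum. CT fusion also has the lower planned power (79% to 83%, Protocol 9.1), and its non-inferiority test must succeed before either superiority test is reached (SAP 9.1). The documents make no comparable statement for SPC.

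**Working it through.** **Inputs from the documents.** SPC success 62% (AMPLEX) versus 60% (ABG); 264 and 132 subjects; margin 12 points; one-sided 5% (SAP 3.2). CT fusion 70% to 75% in both arms (Protocol 9.1).

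**Assumptions not in the documents.** Four equal strata (site by risk), and an additive effect *e* of each factor on the success rate, the same in both arms.

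**Formulas.**
- Unstratified variance: V_un = pA(1-pA)/264 + pB(1-pB)/132.
- Between-stratum variance of the success rate: 2(e/2)² = e²/2. With balance within strata, the true variance is V_st = V_un - (e²/2)(1/264 + 1/132).
- Power, unstratified interval: Φ((d + 0.12 - 1.645·SE_un)/SE_st).
- Power, stratified interval: Φ((d + 0.12)/SE_st - 1.645).
- Type I error, unstratified interval: Φ(-1.645·SE_un/SE_st).

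**Plan's own figures (e = 0).** For SPC, V_un = 0.2356/264 + 0.24/132 = 0.0027106 and SE = 0.05206. Power = Φ((0.14 - 0.0856)/0.05206) = 85.2%, which matches the stated 85% with 396. CT fusion gives 79.1% at 70% and 83.0% at 75%, matching the stated 79% to 83%.

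**SPC at e = 20 points.** V_st = 0.0027106 - 0.02 × 0.0113636 = 0.0024833 and SE_st = 0.04983. The 90% half-width is 8.56 points unstratified and 8.20 stratified. Power is 86.2% versus 87.8%. The unstratified type I error is Φ(-1.719) = 4.3%.

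**All cases, 396 subjects.** Power is unstratified → stratified; the unstratified type I error is in parentheses.

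| Effect of each factor | SPC 62% vs 60% | CT 70% | CT 75% |
|---|---|---|---|
| 0 | 85.2 → 85.2 (5.0) | 79.1 → 79.1 (5.0) | 83.0 → 83.0 (5.0) |
| 10 points | 85.4 → 85.8 (4.8) | 79.4 → 80.0 (4.8) | 83.3 → 83.9 (4.8) |
| 20 points | 86.2 → 87.8 (4.3) | 80.3 → 82.6 (4.2) | 84.4 → 86.6 (4.1) |

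**Simulation check.** With 200,000 trials per scenario, 40% ankle, 70% with any risk factor and allocation balanced within strata, SPC at 20 points per factor gave power of 86.6% unstratified and 87.9% for Mantel-Haenszel with the Sato variance. Type I errors were 4.2% and 4.9%. CT at 70% gave 81.0% versus 83.0%. With no stratum effect, SPC gave 85.8% versus 85.7%. Across the simulated scenarios the Sato interval's type I error stayed between 4.6% and 5.1%. When allocation was not stratified, the unstratified interval ran at 5.0%, which confirms that the conservatism comes from the balance within strata.

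**The case against.** The strongest reply is that nothing is broken. The unstratified interval is prespecified, the same in both documents, conservative, and matched to the sample-size calculation. That stands, and it is why this is an improvement to make and not an error to correct.

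The larger gains also need strong strata. Twenty points for each factor means 40 points between the extreme strata (95% versus 55% for CT at 75%), and Protocol 1.3 supports only the risk factor, not hindfoot versus ankle. The risk stratum is also diluted, because SAP 7.1.5 counts any smoking history and BMI of 30 or more. If only the risk factor matters, V_st loses e²/4 in place of e²/2. At 396 subjects the gains are then 0.2 to 0.3 points for a 10-point effect and 0.8 to 1.1 for 20 points (SPC 85.7% to 86.5%, CT at 70% 79.7% to 80.8%).

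In addition, LOCF with failure as the fallback gives every operated subject a status, so the analysed number is nearer 480. There, 20 points per factor gives 91.5% to 92.6% for SPC and 86.7% to 88.5% for CT at 70%. With the risk factor alone, CT at 70% goes from 86.1% to 87.0%. All of this limits the size of the gain but does not remove it.

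Two further points are fair. The 9.3.2 models use a four-level fusion-site factor and no center term, so they do not mirror the randomization exactly. And the one-factor Mantel-Haenszel analyses already touch each component of the strata. They still leave no planned analysis of either endpoint on the joint strata as randomized.

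**Conclusion.** The concern holds as a matter of efficiency and internal consistency. Validity is not threatened, and the planned power is not overstated. With 396 subjects, four equal strata and additive effects, the power forgone is 0 to 0.6 points for effects up to 10 points per factor and 1.6 to 2.3 points at 20. It is about half that if only the risk factor is prognostic. The documents support prognostic strata for CT fusion and do not address SPC. They give no stratum rates, so the range cannot be narrowed. Because the stratified interval costs almost nothing when the strata are irrelevant, the change is worth making.

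**What to change.** In SAP 9.2.1 and 9.3.1, and in the protocol synopsis, 9.6.2 and 9.6.3, define the risk difference and its 90% and 95% intervals as a Mantel-Haenszel weighted difference over the four surgical-site by any/none-risk strata as randomized, and name the variance estimator (for example Sato). Leave center out of the analysis strata: 50 centers × 4 cells is up to 200 cells, or 480/200 = 2.4 subjects each. Keep the unstratified interval as a sensitivity analysis.

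The tipping-point text in SAP 9.2.2 must follow: "The tipping point analysis will assess the non-inferiority in all possible combinations of missing data imputation". There, a pair of success counts fixes the unstratified result but not a stratified one. Either keep the grid on the unstratified interval and say so, or state how imputed successes are allocated to strata. The note that the LOCF primary result is one point on the grid must agree with that choice.

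If the sponsor prefers to leave the primary analysis as it is, add the four-stratum Mantel-Haenszel interval as a named sensitivity analysis for both endpoints. Either choice should be fixed before outcomes are examined by arm.

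No new data are needed. Changing the deciding analysis requires a protocol amendment or an entry in SAP section 12, which now reads: "There is no deviation from the planned analysis described in the protocol". If the strata turn out not to matter, the loss in simulation is about 0.1 point of power.

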3.2 Determination of Sample Size

Assuming true success rates of the primary endpoint to be 60% for ABG and 62% for AMPLEX groups, respectively, 396 subjects are needed to maintain 85% power to demonstrate non-inferiority of AMPLEX to ABG with a non-inferiority margin of -12% (AMPLEX minus ABG) at a type I error rate of 1-sided 5% in a 2:1 randomization (264 for AMPLEX and 132 for ABG). To maintain this sample size for the 78-week completers (per the FDA's recommendation) after taking account for approximately 15% discontinuation (including lost to follow-up) rate, a total of 480 subjects (320 for AMPLEX and 160 for ABG) will be randomized.

In this calculation, the true success rate for AMPLEX is assumed to be slightly higher than that for ABG because of the potential benefit for AMPLEX on the absence of significant graft harvest site pain component. The assumption on the true success rate for ABG is made based on the clinical endpoint results in DiGiovanni et al. (2013)¹ ([1](#)) and the Augment SSED (2015) ([4](#)). These data indicate relatively high success rates for each component at Week 52. The estimated success rate as a composite endpoint is approximately 60%, when it is assumed that the success of each component is independent of each other.

4 Subject Disposition

All subjects who signed the informed consent form will be considered screened for the trial. All screened subjects who discontinued from the trial prior to randomization will be classified as screening failures. Screening failures and their primary reason for screening failure will be tabulated. The number of screened subjects will be used as the denominator when the percentage of each primary reason for screening failure is calculated.

Subjects who were randomized, received the procedure (surgery), were treated with the graft material, prematurely discontinued from the study, and completed the study will be tabulated with the reason of premature discontinuations for all randomized subjects. Similar tabulations will be made by investigational site and by region (US or Canada).

The number and percentage of subjects who attended Visits 2, 3, 4, 5, 6, 7, and 8 will be tabulated for all randomized subjects based on the nominal visit data recorded on the eCRF.

The time from randomization to discontinuation will be summarized by the Kaplan-Meier method.

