7.1.6 Other Baseline Characteristics

Baseline weight-bearing pain, FAAM-ADL score, SF-12 physical component summary (PCS), and SF-12 mental component summary (MCS) will be summarized.

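### SPC success depends by construction on baseline pain and baseline FAAM-ADL, but no planned analysis adjusts the SPC treatment comparison for either score

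*SAP*

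**What the plan says.** SAP 9.2.1 counts a subject as an SPC success only if all five criteria are met. Two of them are changes from baseline: a fall of at least 20 mm in weight-bearing pain and a gain of at least 8 points in FAAM-ADL. The treatment difference is a plain difference of proportions, with no covariates: "The CI will be constructed with the normal approximation to the binomial". The protocol fixes the same interval in its synopsis (Efficacy Analysis) and in 9.6.2.

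The sensitivity analyses are in SAP 9.2.2:

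- The as-treated, ITT and per-protocol analyses repeat the crude method.
- Missing-equals-failure and the tipping-point analysis change only how missing status is filled.
- Multiple imputation uses treatment, unnamed baseline characteristics and earlier outcomes as predictors, then applies the crude method to each completed dataset.
- The Mantel-Haenszel analyses control one factor at a time: age, gender, race, obesity, diabetes, previous surgery, smoking, primary etiology, affected side, fusion site, investigational site and region. Neither baseline score is listed.

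Both scores are available. SAP 7.1.6 states: "Baseline weight-bearing pain, FAAM-ADL score, SF-12 physical component summary (PCS), and SF-12 mental component summary (MCS) will be summarized". When the same two instruments are analysed as continuous secondary endpoints (SAP 9.3.2), the model contains "treatment, time, treatment-by-time interaction, baseline value, presence of non-union risk factors" and fusion site.

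The sample size (SAP 3.2) assumes success rates of "60% for ABG and 62% for AMPLEX groups" and a "non-inferiority margin of -12% (AMPLEX minus ABG"), and concludes that "396 subjects are needed to maintain 85% power".

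**The concern.** Protocol 4.1.1 admits subjects with weight-bearing pain of 40 mm or more. A subject who enters at 40 mm must lose half of that pain to gain 20 mm (20/40 = 50%); one who enters at 90 mm needs a fall of 22% (20/90). FAAM-ADL runs from 0 to 100 (SAP Appendix 2), and Protocol 4.1 sets no entry limit on it. A subject who starts above 92 cannot gain 8 points and fails whatever graft is used.

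Randomisation is stratified by center, surgical site and nonunion risk factors, so nothing in the design balances either score beyond chance. A chance difference between arms becomes part of the difference that is read against -12 points. The SAP has no pre-specified SPC estimate that would show how much of the result it accounts for, and an adjusted estimate produced afterwards would carry less weight. The SAP accepts baseline adjustment for the continuous versions of these endpoints but not for the composite on which the trial is judged.

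**Working it through.** **1. Inputs from SAP 3.2.** Success rates 0.60 (ABG) and 0.62 (AMPLEX); margin 0.12; "type I error rate of 1-sided 5% in a 2:1 randomization (264 for AMPLEX and 132 for ABG").

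**2. The plan's own figure.**
- Variance of the crude difference = 0.62 × 0.38/264 + 0.60 × 0.40/132 = 0.000892 + 0.001818 = 0.002711, so SE = 5.206 points.
- Power = Φ[(0.12 + 0.02)/0.05206 − 1.645] = Φ(1.044) = 85.2%.

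The stated 396 subjects and 85% power therefore reproduce with the crude interval.

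**3. How much the two scores could explain.** The documents give no mean, SD or correlation for either score, so R², the share of SPC variance they explain, has to be assumed. Two simulations were run.

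- First: baseline pain mean 65, SD 15, at least 40 mm; Week-52 pain mean 28, SD 26; FAAM-ADL rising from 52 to 74. R² was 0.117, 0.073, 0.044 and 0.023 for baseline to Week-52 correlations of 0, 0.2, 0.35 and 0.5.
- Second: baseline pain mean 65, SD 15; baseline FAAM-ADL mean 50, SD 17; Week-52 means 23 and 76. R² was 0.127, 0.080, 0.044 and 0.017 for correlations of 0, 0.2, 0.4 and 0.6.

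In both, the link weakens as baseline and Week-52 scores become more correlated. At correlation 0.2 in the first, SPC success was 37% below 50 mm and 64% above 75 mm at baseline.

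**4. Effect of adjustment.** Approximation: adjusted SE = crude SE × √(1 − R²). The 90% half-width is 1.645 × SE. The crude analysis would need 396/(1 − R²) − 396 extra subjects to match the adjusted one.

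| R² | SE at 264/132 (points) | 90% half-width | Power at 264/132 | Extra subjects | Power at 320/160 |
|---|---|---|---|---|---|
| 0 | 5.21 | 8.56 | 85.2% | 0 | 90.6% |
| 0.023 | 5.15 | 8.46 | 85.9% | 9 | 91.2% |
| 0.044 | 5.09 | 8.37 | 86.5% | 18 | 91.7% |
| 0.073 | 5.01 | 8.25 | 87.5% | 31 | 92.4% |
| 0.117 | 4.89 | 8.05 | 88.8% | 52 | 93.4% |

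The last column matters because the mITT set (SAP 6.2) includes every subject once surgery is initiated, and SAP 9.2.1 fills missing Week-52 status. The analysed number can therefore approach the 480 randomised. The crude SE at 320/160 is √(0.62 × 0.38/320 + 0.60 × 0.40/160) = 4.73 points. The column keeps the assumed 60% and 62%, which imputed failures could change.

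**5. Chance imbalance.** With 264 and 132 subjects, a standardised baseline difference between arms has SD √(1/264 + 1/132) = 0.107. Under the step 4 approximation, the part of the crude estimate's sampling error that comes from imbalance in the two scores has SD = SE × √R²: 5.21 × √0.023 = 0.8 points to 5.21 × √0.117 = 1.8 points. A 2 SD imbalance therefore moves the estimate by 1.6 to 3.6 points. For scale, non-inferiority needs an observed difference above −12 + 8.56 = −3.4 points, which is 5.4 points below the assumed +2.

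**6. Validity of the crude interval.** In the second simulation (2,000 trials of 264/132 per setting, no true difference), the crude 90% interval covered 89.5% to 89.9%. The Monte Carlo standard error is √(0.9 × 0.1/2000) = 0.7 points, so this is nominal. Linear adjustment reduced the SD of the estimate from 5.26 to 4.94 points at correlation 0, but only from 5.05 to 5.04 at correlation 0.6. The realised gain was slightly below what step 4 predicts.

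**The case against.** The strongest reply is that the plan contains no error. Under randomisation the crude risk difference is unbiased and its interval already allows for chance imbalance; step 6 bears this out. The sample size reproduces without adjustment, and 480 less "approximately 15% discontinuation (including lost to follow-up) rate" leaves 480 × 0.85 = 408, above 396. The gain rests on correlations that nobody has stated: at R² of 0.023 it is 0.7 power points at 264/132 and 0.6 at 320/160. Imbalance would be visible in the baseline tables, and SAP 9.3.2 gives baseline-adjusted differences on both underlying scores. A simple pre-specified risk difference is a legitimate primary analysis.

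All of that stands, and it sets the weight of the point. It does not remove it. Baseline tables show an imbalance but not its effect on SPC, and the secondary ANCOVAs estimate a different quantity.

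A reader might also infer that no sensitivity analysis uses the two scores at all. The documents do not support that. The imputation model takes baseline characteristics as predictors, and SAP 7.1.6 files both scores under a heading of that kind. The predictors are not named, however, and the comparison after imputation is still crude.

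**Conclusion.** The point holds as one of precision and of protection against chance imbalance. SPC success depends on both baseline scores by definition, and no planned analysis adjusts the SPC treatment comparison for them.

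The size is modest: about 0.7 to 3.6 power points at 264/132 and 0.6 to 2.8 at 320/160. This rests on an assumed R² of 2% to 12% and on the linear-model approximation for the standard error. If baseline and Week-52 scores are strongly correlated, the gain could be negligible.

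Two stronger readings should be resisted. One is that a baseline imbalance biases the primary result or inflates type I error; it does not, because such imbalance is ordinary sampling error that the interval covers. The other is that the trial is underpowered as planned; the stated power reproduces with the crude interval.

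**What to change.** Before database lock and without reference to outcomes by arm, pre-specify in SAP 9.2 an SPC risk difference obtained by standardisation (g-computation) from a logistic model with treatment, baseline weight-bearing pain VAS and baseline FAAM-ADL. Give it a robust or delta-method 90% CI read against −12% and a 95% CI read against 0. The target remains the marginal risk difference, so the margin keeps its meaning. Also name both baseline scores as predictors in the multiple-imputation model.

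- **Minimum:** add the analysis to SAP 9.2.2 as a sensitivity analysis. This costs SAP wording and a few lines of code, with no new data.
- **Fuller option:** make it primary and keep the crude interval as the sensitivity analysis. This costs more than SAP wording, because the protocol synopsis and Protocol 9.6.2 both fix the crude interval and would need amending. The statement in SAP section 12 that there is no deviation from the protocol analysis would need updating.
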